CTC V4 Grade	1	2	3	4	1	2	3	4	1	2	3	4
Arthritis						1						
Bladder infection		1										
Chills	1	1				2				2		
Constipation	1								1			
Diarrhea	2				1				1	1		
Dizziness					2							
Dry mouth	1				2							
Dry skin						1						
Edema limbs	1	1										
Fatigue	1	1							2	1		
Fever	2	2			1	1			2	2		
Headache	1				1							
Hypotension		1				1			1			
Nausea	2				2				3			
Pulmonary edema		1										
Rash maculo-papular	2								2			
Vomiting	2				1				2			

Abbreviated Title: IL-15+Mogamulizumab

Version Date: 11/16/2020

Table 5: Laboratory abnormalities possibly, probably, or definitely related to research (5-day CIV cohort) excluding single grade 1 events

	3 µg/kg n=4				4 µg/kg n=3				5 µg/kg n=4			
CTC V4 Grade	1	2	3	4	1	2	3	4	1	2	3	4
Anemia			2			2			1	1	1	
ALT increased	1	1			1	1			3			
AST increased		2			2				4			
Alkaline phosphatase		1			1		1		2	1		
Hyperbilirubinemia	1	1				1			1		1	
Hypoalbuminemia		2			1	1			2	2		
Creatinine increased					1				1	2		
Hyperglycemia										1		
Hypernatremia	2										1	
Hyponatremia	1		1		2				3			
Hypocalcemia	1				1				4			
Hypokalemia	2	1							1		2	
Hypomagnesemia					1				3			
Hypophosphatemia		1	2			2				1	2	
Lymphocytosis				2				2			1	2
Lymphopenia		1				1	1			2	1	1
Neutropenia	1				1		1			1		
Thrombocytopenia		2			2				1	1		
Leucopenia		2				1	1		1	1	1	

1.2.5.2 Preclinical Trials of IL-15 with Anticancer Monoclonal Antibodies to Augment their ADCC

While the *in vivo* effects of IL-15 in cancer patients are still not entirely clear, the initial clinical data has demonstrated that to achieve its potential in the treatment of cancer, IL-15 will have to be used in combination with other therapeutic agents. In light of the data, from preclinical animal models and clinical trials, of the capacity of IL-15 to increase the number of activated NK cells, T cells and, monocytes this information supports the administration of IL-15 with antitumor monoclonal antibodies to augment their ADCC against tumor cells. To further investigate this strategy, the [name] Laboratory used an immunocompetent syngeneic mouse model of B-cell lymphoma to investigate the combination of IL-15 with rituximab.[\(40\)](#) Wild-type CD56 and BL/6 mice were inoculated intravenously with EL4-CD20 cells, a mouse lymphoma line transfected with human CD20 and the mice were distributed into 4 treatment groups (control, IL-15 alone, rituximab alone and the combination) of 10 mice each. IL-15 (5 µg/mouse) was administered 5 times per week for 4 weeks beginning 3 days after EL4-CD20 inoculation. In cohorts receiving rituximab, the monoclonal antibody was given once per week for 4 weeks starting 5 days after EL4-CD20 inoculation. IL-15 or rituximab monotherapy prolonged survival of mice when

Abbreviated Title: IL-15+Mogamulizumab

Version Date: 11/16/2020

compared to the control group ($p < 0.05$) but the combination of IL-15 and rituximab showed the greatest prolongation of survival compared to monotherapies (< 0.01), so that 75 days after tumor inoculation 90% of the combination treatment group were still alive in contrast to 30% survival from the monotherapy groups and no surviving mice in the control group (Figure 3). In a parallel preclinical trial, the [name] Group administered a combination therapy of alemtuzumab with rhIL-15 in the MET-I bearing xenograft model in wild-type SCID/NOD mice (Figure 4). Again, there was an augmentation of survival of the combination of IL-15 with alemtuzumab compared to either element alone.

In summary, clinical trials in humans indicate that IL-15 administered by CIV is well tolerated and is associated with an increase in the number of NK cells. Furthermore, studies combining monoclonal antibodies with IL-15 in syngeneic and xenogeneic murine tumor models provide scientific support for the combination of antitumor monoclonal antibodies with IL-15 in patients with chronic and acute lymphoma forms of ATLL. All previous trials in patients with acute ATLL have been closed for patient accrual.

[figure not shown]

Figure 3:The effect of Rituximab and human IL-15 treatment of CD20+ Lymphoma

[figure not shown]

Figure 4:The effect of Alemtuzumab and human IL-15 treatment of ATL cell line MET-1

Abbreviated Title: IL-15+Mogamulizumab

Version Date: 11/16/2020

2 ELIGIBILITY ASSESSMENT AND ENROLLMENT

2.1 ELIGIBILITY CRITERIA

2.1.1 Inclusion Criteria

- 2.1.1.1 Patients must have one of the following histologically or cytologically proven relapsed and/or refractory to at least one line of systemic treatment, T-cell malignancies confirmed by the Laboratory of Pathology, NCI: mycosis fungoides/Sézary syndrome, or adult T-cell leukemia (chronic, acute, or lymphoma subtype by Shimoyama criteria, see **Table 1**)
- 2.1.1.2 Patients with CD30+ MF/SS must have relapsed after or become intolerant to treatment with brentuximab vedotin
- 2.1.1.3 A formalin fixed tissue block or 15 slides of tumor sample (archival or fresh) must be available for performance of correlative studies. **NOTE:** Patients must be willing to have a tumor biopsy if prior tissue or adequate archival tissue is not available (i.e., post-enrollment and prior to treatment).
- 2.1.1.4 Disease must be measurable with at least one measurable lesion by RECIL 2017 or mSWAT criteria (see Section **6.3**), or have an abnormal clonal T-cell population detectable by peripheral blood flow cytometry
- 2.1.1.5 Age >18 years

NOTE: Because no dosing or adverse event data are currently available on the use of rhIL-15 in combination with mogamulizumab in patients <18 years of age, children are excluded from this study, but will be eligible for future pediatric trials

- 2.1.1.6 ECOG performance status ≤ 1 (Karnofsky $\geq 80\%$, see **APPENDIX A**)

- 2.1.1.7 Patients must have normal organ and marrow function as defined below:

Absolute neutrophil count	$\geq 1,000/\text{mcL}$
Platelets	$> 100,000/\text{mcL}$
Total bilirubin	$\leq 1.5 \times$ institutional upper limit of normal (ULN)
AST(SGOT)/ALT(SGPT)	$\leq 2.5 \times$ institutional ULN
Serum creatinine	$\leq 1.5 \times$ institutional ULN
OR	
Creatinine clearance	$\geq 50 \text{ mL/min}/1.73 \text{ m}^2$ for patients with creatinine levels >1.5 institutional ULN

- 2.1.1.8 Negative serum or urine pregnancy test at screening for women of childbearing potential (WOCBP)

NOTE: WOCBP is defined as any female who has experienced menarche and who has not undergone successful surgical sterilization or who is not postmenopausal.

- 2.1.1.9 Women of child-bearing potential and men must agree to use adequate contraception (hormonal or barrier method of birth control; abstinence) prior to study entry, for the duration of study participation, and 6 months after completion of rhIL-15 and mogamulizumab administration. Should a woman become pregnant or suspect she is

Abbreviated Title: IL-15+Mogamulizumab

Version Date: 11/16/2020

pregnant while she or her partner is participating in this study, she should inform her treating physician immediately.

2.1.1.10 Ability of subject to understand and the willingness to sign a written informed consent document

2.1.2 Exclusion Criteria

2.1.2.1 Patients with other T-cell leukemias/lymphomas not specified in the inclusion criteria

2.1.2.2 Anti-cancer treatment within 2 weeks of the first dose of rhIL-15 and mogamulizumab (4 weeks for anti-cancer monoclonal antibody or investigational agents, 6 weeks for donor lymphocyte infusion, 100 days for allogeneic stem cell transplant)

2.1.2.3 Systemic treatment for acute or chronic graft versus host disease (GVHD) within 12 weeks of the first dose of rhIL-15 and mogamulizumab

2.1.2.4 Cohort 1 (Dose Escalation) only: history of grade 3/4 GVHD, or active grade 1/2 GVHD regardless of treatment

2.1.2.5 Persisting toxicity related to prior therapy of grade > 1, with the exception of the following: alopecia, sensory neuropathy grade ≤ 2 , or other grade ≤ 2 not constituting a safety risk based on investigator's judgment

2.1.2.6 Patients who are receiving any other investigational agents

2.1.2.7 Current use of immunosuppressive medication, EXCEPT for the following:

- Intranasal, inhaled, topical steroids, or local steroid injection (e.g., intra-articular injection)
- Systemic corticosteroids at physiologic doses ≤ 10 mg/day of prednisone or equivalent; or,
- Steroids as premedication for hypersensitivity reactions (e.g., CT scan premedication)

2.1.2.8 Patients with previous malignant disease other than the target malignancy within the last 3 years with the exception of basal or squamous cell carcinoma of the skin or cervical carcinoma in situ

2.1.2.9 Cohort 1 (Dose Escalation) only: Active or history of any autoimmune disease thought to be unrelated to their malignancy; for Cohort 2 (Dose Expansion), patients with history of autoimmune disease who are not on active immunosuppressive therapy per Section 2.1.2.7 are eligible.

2.1.2.10 Patients with asthma requiring chronic inhaled or oral corticosteroids, or history of asthma requiring mechanical ventilation. Patients with a history of mild asthma that are on or can be switched to non-corticosteroid bronchodilator regimens are eligible

2.1.2.11 Patients with active bacterial infections, documented HIV infection or positive HIV 1/2 antibodies at screening, PCR evidence for active or chronic hepatitis B or hepatitis C, or positive screening HBV/HCV serology without documentation of successful curative treatment (see Section 12.1 for IL-15 administration in HIV positive patients)

2.1.2.12 Presence of uncontrolled intercurrent illnesses including but not limited to ongoing or active infection, symptomatic congestive heart failure, unstable angina pectoris, cardiac arrhythmia, cognitive impairment, active substance abuse, or psychiatric illness/social

Abbreviated Title: IL-15+Mogamulizumab

Version Date: 11/16/2020

situations that in the view of the Investigator would preclude safe treatment and limit compliance with study requirements

- 2.1.2.13 Inability or refusal to practice effective contraception during therapy or the presence of pregnancy or active breastfeeding. Because there is no significant preclinical information regarding the risks to a fetus or a newborn infant, all pregnant or breastfeeding woman will be excluded from participation in this trial
- 2.1.2.14 History of allergic reactions attributed to compounds of similar chemical or biologic composition to rhIL-15 or mogamulizumab, unless felt to be in the best interests of the patient in the opinion of the investigator
- 2.1.2.15 Patients who received a live vaccine within 30 days of planned start of study therapy. Vaccination with a live vaccine while on trial is prohibited. **NOTE:** Seasonal influenza vaccines for injection are generally inactivated flu vaccines and are allowed; however intranasal influenza vaccines (e.g., Flu-Mist®) are live attenuated vaccines, and are not allowed

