1.2.1.1 Treatment of ATLL

There are no curative therapeutic options for patients with ATLL outside of early allogeneic stem cell transplantation, ideally immediately after achieving a complete response to first-line chemotherapy.(3) Prognosis of ATLL relapsed or refractory to front-line therapy is dismal(4), and experience with the standard combination chemotherapeutic regimens known to be useful in the treatment of the more common aggressive B-cell non-Hodgkin lymphomas or acute lymphoblastic leukemia has been disappointing. In North America, the majority of patients with the three more aggressive categories of ATLL (severe chronic, acute, and lymphoma subtype) are still treated with CHOP-based regimens (cyclophosphamide, Adriamycin, vincristine and prednisone) with or without interferon and zidovudine.(5) In countries where ranimustine and vindesine are available, and which have the infrastructure for a more intensive chemotherapy regimen, the LSG15 protocol (VCAP-AMP-VECP) is an option shown to be superior to biweekly CHOP in a phase III trial (complete response [CR] rate 40% v. 25%, 3-year OS 24% v. 13%).(6) A meta-analysis showed that the addition of interferon and zidovudine to first-line therapy improved OS of patients with acute, chronic, and smoldering subtypes(7), but there was a lack of efficacy in patients with relapsed disease.

There are no US FDA-approved drugs for relapsed/refractory ATLL, and no randomized phase III trials have been conducted in this patient population. Mogamulizumab (KW-0761), a monoclonal antibody targeting CCR4, is approved in Japan for treatment of CCR4-positive ATLL. In a phase II trial of 27 Japanese patients with relapsed ATLL, overall response rate (ORR) was 50% (95% CI 30% to 70%), median progression-free survival (PFS) was 5.2 months, and median OS 13.7 months.(8) An international randomized phase II study of mogamulizumab versus investigator-choice chemotherapy in 71 patients from the US, Europe, and Latin America with aggressive relapsed/refractory ATLL showed confirmed ORR (response lasting ≥8 weeks) to be 11% versus 0%, and best ORR 28% versus 8% (*in press*).

Lymphoid Malignancies Branch (LYMB) conducted a phase II trial of alemtuzumab (Campath), an anti-CD52 monoclonal antibody, in 29 patients with relapsed chronic, acute, and lymphomatous

Abbreviated Title: IL-15+Mogamulizumab

Version Date: 11/16/2020

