3.3.2.2 Treatment modifications for dermatologic toxicity

Table 10: Treatment Modifications for Dermatological AEs

Dermatological irAEs		
Rash	Initial Management	Resuming protocol treatment
Grade 1 Covering $<10\%$ of body surface area	Continue protocol therapy Consider topical steroids	N/A
Grade 2 to 3 Covering $>10\%$ of body surface area	Hold protocol therapy Administer topical steroids for at least 2 weeks	Rash improves to Grade ≤ 1
Grade 4 Life-threatening consequences; Stevens-Jonson syndrome (SJS) or	Hold protocol therapy for suspected SJS/TEN Permanently discontinue protocol therapy if SJS/TEN has been	SJS/TEN has been excluded and the rash improves to Grade ≤ 1

Abbreviated Title: IL-15+Mogamulizumab

Version Date: 11/16/2020

Dermatological irAEs		
Rash	Initial Management	Resuming protocol treatment
toxic epidermal necrolysis (TEN)	confirmed or if there are life-threatening consequences	

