4 CONCOMITANT MEDICATIONS/MEASURES

Medications or vaccinations specifically prohibited in the exclusion criteria are not allowed during the ongoing trial with the exception of oral or parenteral steroids if they are administered more than 7 days before the start of or more than 7 days after the end of IL-15 infusion. If there is a clinical indication for a prohibited medication/ measure during the trial, discontinuation from trial therapy may be required.

For premedication and supportive care measures, see Sections [3.2.1](#), [3.2.2](#), and [3.2.3](#).

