6.3.2 Response Criteria for MF/SS

Global Response (GR) score (**APPENDIX C**) will be used for assessing response in patients with CTCL ([41](#)). GR score incorporates separate responses in each component of the TNBM staging (i.e., skin, nodes, viscera and blood; **APPENDIX C**). No patient with a global OR should have less than a PR in the skin.

Abbreviated Title: IL-15+Mogamulizumab

Version Date: 11/16/2020

The mSWAT ([19](#)) is an instrument utilized to track the skin tumor burden in MF/SS. It measures the percentage total body-surface area (TBSA, %) involvement separately for patches, plaques, and tumors within 12 body regions using the patient's palm and fingers representing 1% of TBSA. Patients with erythroderma are assessed for percentage of TBSA involved with patches and/or plaques. The percentage of TBSA for each lesion type is multiplied by a number (patch = 1, plaque = 2; tumor = 4) and summed to derive the mSWAT score. The mSWAT for each patient will be determined by the same individual at all study visits.

A complete response (CR) requires 100% clearing of skin disease and a partial response (PR) requires $\geq 50\%$ reduction in the mSWAT score compared with baseline. CR/PR requires confirmation by repeat assessment after ≥ 4 weeks. Stable disease is defined as less than 50% reduction to less than 25% increase in the mSWAT score compared with baseline. PD is defined as $\geq 25\%$ increase in the mSWAT score from baseline or $\geq 50\%$ increase in the sum of the products of the greatest diameters of pathologically positive lymph nodes compared with baseline.

Time to response is the time from the first treatment dose until the patient first meets the criteria for a 50% decrease in the GR score. The duration of response (DOR) is the time from first CR/PR until the GR score is increased from nadir to more than 50% of the difference between the baseline and nadir scores. Time to progression (TTP) is the time from start of treatment until PD. If patients goes off treatment for any purpose, this date is used for determination of TTP and/or DOR.

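### The response rules ignore steroids that the plan permits or directs, so an improvement under a newly started or increased steroid, mainly in skin, can be scored as CR or PR

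*Combined protocol and SAP*

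**What the plan says.** **Entry.** Section 2.1.2.7 excludes current immunosuppression but exempts "Intranasal, inhaled, topical steroids, or local steroid injection (e.g., intra-articular injection" and "Systemic corticosteroids at physiologic doses ≤ 10 mg/day of prednisone or equivalent; or". It also exempts steroid premedication, for example before CT. It sets no condition that use be stable before the baseline assessment.

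**On study.** Section 4 carries the entry prohibitions into the treatment period, "with the exception of oral or parenteral steroids if they are administered more than 7 days before the start"; the same 7-day distance applies once an infusion has finished. No dose, duration or indication is given. Section 4.2 bars other therapy for the disease but allows other medication that the investigator thinks necessary.

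**Rash.** Table 10 (section 3.3.2.2) says "Consider topical steroids" for grade 1. For grade 2-3 it holds protocol therapy and says "Administer topical steroids for at least 2 weeks". Treatment may resume once the rash is grade 1 or less. Section 3.1.1.2 exempts grade 3 rash from the DLT definition, so these patients can stay on study and in the response assessment.

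**Response.** For MF/SS, section 6.3.2 says "A complete response (CR) requires 100% clearing of skin disease and a partial response (PR) requires" at least a 50% fall in mSWAT from baseline, repeated after 4 weeks or more. A global response needs at least a PR in skin. For ATLL, Table 12 asks that each criterion be present for at least 4 weeks. Section 6.3.4 takes the best response up to progression. None of these, nor Appendix C, evaluability (section 10.3.2) or the analysis (sections 10.4.1, 10.4.3), mentions steroids.

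**Recording.** Section 4.1 requires concomitant medication on the CRF, but for changes during the trial the dose and date are only optional entries.

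**The concern.** The trial has one treatment per dose level, no control arm and investigator-assessed response. Only the response rules can separate a study-drug effect from the effect of something else given meanwhile. Skin decides whether an MF/SS patient can be a responder at all, and skin is the organ to which Table 10 directs steroids, at a time when study treatment is on hold. Section 14.2.2 notes that most immune-mediated reactions to mogamulizumab were managed with interruption, corticosteroids and supportive care, so steroid use is foreseeable. The protocol also names prednisone within a lymphoma regimen, the "CHOP-based regimens (cyclophosphamide, Adriamycin, vincristine and prednisone" combination in section 1.2.1.1. If an improvement under a new steroid is counted, ORR and DOR are attributed to the combination more firmly than the data allow. Stopping a steroid after baseline could act in the other direction.

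**Working it through.** The plan states no figure on this point, so there is none to reproduce. The check follows the text and then sizes one misattributed response.

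**1. Can a steroid-period improvement meet PR as written?** Take an MF/SS patient with grade 2-3 rash. Therapy is held and topical steroids run for at least 2 weeks, with no stated maximum. At the next 8-weekly evaluation mSWAT is down by 50% or more. Section 6.3.2 scores a skin PR. A repeat after 4 weeks or more confirms it, and neither assessment has to be off steroids. Section 10.3.2 needs measurable disease, one cycle and a re-evaluation, all met. Nothing in sections 6.3 or 10.4 removes or flags the patient.

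**2. When are systemic steroids allowed?** rhIL-15 runs for 120 hours (section 3.3.1) in a 28-day cycle. The gap between infusions is 28 − 5 = 23 days. If both 7-day buffers apply, 23 − 14 = 9 days remain, about Days 13 to 22. With the 26-day minimum cycle (section 3.2), 26 − 5 − 14 = 7 days remain. After the last infusion there is no later bound. The latest permitted point in Cycle 2 is about study Day 28 + 22 = 50. The first evaluation, at 8 weeks ± 2 days, falls on about Days 55 to 59, so 5 to 9 days later.

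**3. How many patients might be exposed?** The documents give no rate of steroid use. Section 3.1.1.2 gives an expected grade 3 rash rate of 10% for mogamulizumab.
- Expected number: 0.10 × 12 = 1.2 patients; 0.10 × 18 = 1.8.
- Chance of at least one, 1 − (1 − q)^n, with patients independent: at q = 10%, 1 − 0.9^12 = 72% and 1 − 0.9^18 = 85%. For assumed q = 5%, 46% and 60%; for assumed q = 20%, 93% and 98%.

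These are chances that a patient comes under the Table 10 instruction. They are not chances of a misattributed response.

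**4. What does one misattributed response do?** Section 10.2 gives 12 patients at the MTD and at most 18 evaluable. The shift is 1/12 = 8.3 points or 1/18 = 5.6 points. The Agresti-Coull interval of section 10.4.1 uses ñ = n + z², p̃ = (x + z²/2)/ñ and limits p̃ ± z√(p̃(1 − p̃)/ñ), with z = 1.96. For illustrative counts:
- 4/12: p̃ = 0.374; ORR 33.3%, interval 13.6% to 61.2%.
- 5/12: p̃ = 0.437; ORR 41.7%, interval 19.3% to 68.1%.
- 5/18: p̃ = 0.317; ORR 27.8%, interval 12.2% to 51.2%.
- 6/18: p̃ = 0.363; ORR 33.3%, interval 16.1% to 56.4%.

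**The case against.** The case on the other side is substantial, and several parts of it stand.

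- **Safeguards exist.** Confirmation or persistence over 4 weeks removes a brief effect, and on schedule most of each cycle lies outside the systemic window. This stands for short courses. It does not cover sustained or repeated topical use, or systemic use after the last infusion.
- **Entry is controlled.** Section 2.1.2.2 excludes anti-cancer treatment within 2 weeks, and a steroid continued unchanged is already in the baseline. This stands, so the concern is confined to steroids started or increased afterwards (or stopped, in the reverse direction).
- **Some endpoints already have a rule.** For MF/SS, section 6.3.2 uses the off-treatment date for TTP and DOR, and section 4.2 removes patients who need other disease therapy. EFS counts alternative lymphoma therapy. This stands, but a hold for rash is not stated to be off treatment, and ORR has no such rule.
- **The effect is unproven.** Nothing in the documents shows that topical or brief systemic steroids halve mSWAT or nodal size; prednisone appears only as one drug of four. This stands, and it is why the point is that a steroid effect can be scored, not that it will be.
- **ORR is secondary, with no null rate or decision rule, and one patient moves it by less than its interval's half-width.** True, and it limits the weight of the point. The interval covers sampling error only, however, and not misattribution.
- **Affected patients could be listed at reporting from the CRF.** Only in part, because dose and dates of changes need not be recorded.

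**Conclusion.** The gap is real and modest. As written, CR or PR can be credited to the study drugs when the improvement arose under a steroid started or increased since baseline. The clearest route is skin in MF/SS. The size is 8.3 points of ORR per patient at n=12 and 5.6 at n=18. The number of such patients is unknown. About 1 in 12 coming under the Table 10 instruction assumes that the quoted 10% grade 3 rash rate holds here; grade 2 rash would add to it by an amount that the documents do not give. No power or error rate is affected.

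A reader might infer more, and the documents do not support it:
- *Steroids are free at any dose between infusions.* There is no dose cap, but the 7-day separation leaves about 9 days of the cycle.
- *Steroids are required for rash in general, and so affect nodes and blood.* The instruction is topical and for grade 2-3 only. An effect on nodes or blood would have to come through the systemic allowance.
- *A third or more of patients will need them.* This could be read from the four maculopapular rash entries in the 5-day rhIL-15 cohort of 11 (the table before Table 5). All four stand in grade 1 columns, where topical steroids are only to be considered.
- *No time-based endpoint has a rule.* MF/SS TTP and DOR, and EFS, do in part.

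**What to change.** Keep the response definitions in section 6.3 and the main ORR as they are. No change to which steroids may be given is proposed.

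1. In sections 2.4 and 4.1, make type, dose, start date and stop date of topical and systemic steroids required CRF items at baseline and at each response assessment.
2. In section 10.4.3, add a sensitivity ORR and DOR. A CR or PR first met or confirmed while on, or within 4 weeks after, a steroid started or increased since baseline counts as non-response. It is kept if a later scheduled assessment, at least 4 weeks after return to baseline steroid use, still shows it. Exclude single-dose premedication, so that a patient premedicated for each contrast scan is not caught. State from which date DOR runs for a response kept in this way.
3. List the affected patients with the steroid, its dates and the assessments concerned.

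The cost is a few CRF fields and one extra tabulation; existing visits are used, so no new assessment is needed. The drawback is that some true responses will be left out of the sensitivity figure. It should therefore be read beside the main ORR as a lower reading and not replace it.
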